1. OBJECTIVES OF THE INTERIM ANALYSIS F1

- 1. To measure and compare peanut intake and reactions to peanut (accidental or intentional ingestion) from end-of-treatment (T1 of PPOIT-003 study) to 24 months (F1) post-treatment:
 - in PPOIT vs OIT vs placebo and
 - in subjects with SU vs DWSU vs allergic.
- 2. To compare change from baseline in quality of life (PPOIT-003 study entry) at 24 months (F1) posttreatment:
 - in PPOIT vs OIT vs placebo groups and
 - in subjects with SU vs DWSU vs allergic.

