No formal sample size calculation is being conducted for the follow-up study. A maximum of two hundred and one (201) participants will be recruited from PPOIT-003 trial (PPOIT n=79; OIT n=83; placebo n=39).

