For continuous outcomes, the mean difference between treatment groups will be obtained by using GLM to account for clustering by site, adjusted by the age group at randomisation (1-5 years; 6-10 years) and SPT wheal size (\leq 10mm; >10mm). The median difference using quantile regression model to adjust for the stratification factors if not normally distributed.

We will also compare the QoL scores using a mixed model applied to the data at 4 timepoints (T0, T1, T3/F0, F1) and account for clustering by study site, with fixed effects for treatment, age group at randomisation and SPT wheal size, and a random effect to allow for repeated measures for each individual.

ESTIMATION OF EFFECTS (BETWEEN CLINICAL OUTCOME GROUPS)

For binary outcomes, a binary regression model will be used.

For continuous outcomes, the mean difference between the clinical outcome groups will be obtained by using linear regression. Adjusted linear regression will be used to adjust for baseline QoL score in outcome I. The median difference using quantile regression model if not normally distributed.

HANDLING OF MISSING DATA

It is anticipated that 25% of children will not continue to participate the follow-up, due to participant attrition and parent/guardian non-response. The available case analysis will be the

(FORM: SAP template interim analysis/Version 1.1)

primary one. A sensitivity analysis using Inverse Probability Weighting (IPW) and Multiple Imputation (MI) techniques will be used to handle the missing data (details in section below).

SENSITIVITY ANALYSIS

The sensitivity analysis will be performed on an intention-to-treat basis including all the children whose parent/guardian consented for follow-up, with IPW and MI techniques used to handle the missing data. It is anticipated that 25% of the original sample of 201 children will have follow-up outcomes missing. In such situations, we will use both MI combined with IPW techniques (Seaman, S.R., White, I.R., Copas, A.J. and Li, L., 2012. Combining multiple imputation and inverse-probability weighting. Biometrics, 68(1), pp.129-137.) as a sensitivity analysis. It involves two major steps:

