Step 1, calculation of Inverse Probability Weights: Inverse probability weights will be calculated by treatment group using the whole sample of 201 children adopting a logistic regression model predicting participation at F1, using the following baseline variables (with no missing values): age at randomisation and SPT wheal size, clinical outcome at T2 (SU, DWSU without SU or Allergic) Once inverse probability weights are obtained, only children whose parent/guardian consented for follow-up will included in the following step, and in the final analyses.

Step 2, multiple imputation of missing data on those who participated in the F1 follow-up: The frequency and patterns of missing data will be examined. Missing values of included participants will be multiply imputed: multiple imputation models will be specified including all variables included in the analysis models (baseline stratification factors) as well as all the outcomes collected at T3/F0, and F1 follow-up. Thirty completed data sets will be imputed using multivariate normal regression including all the participants who participated in the F1 follow-up. Each dataset resulting from the multiple imputation model (a "quasi-complete dataset" because the data are complete for the included participants, but not for those excluded from MI due to not participating in the F1 follow-up) is then analysed using IPW derived at step 1. IPW reweights data so that it accounts for characteristics of excluded participants (those whose parent/guardian did not consent for the follow-up and are missing all outcome data).

By imputing for participants with few missing values, while using inverse probability weights to account for excluded participants with all missing outcome data, IPW/MI should maintain the efficiency advantage of MI while avoiding possible bias from incorrectly imputing larger blocks of data.

All outcomes listed in Table 2 will be analysed using IPW/MI as a sensitivity analysis.

SUB-GROUP ANALYSIS – AGE GROUP AT SCREENING OF PPOIT003

Available cases will be analysed by subgroups according to their age group at screening of PPOIT003 (0-5 years / 6-10 years) for all outcomes.

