We will also compare the QoL scores between treatment groups using a mixed model applied to the data at 4 timepoints (T0, T1, T3/F0, F1) and account for clustering by study site, with fixed effects for treatment, age group at randomisation and SPT wheal size, and a random effect to allow for repeated measures for each individual.

SIGNATURES PAGE

Signature of Group Leader:

[name]

Date 04 -Jun - 2022

Print Name

[name]

Signature of Principal Investigator:

ale

Date 31-May-2022

Print Name

[name]

Signature of Trial Statistician:

Print Name

[name]

Date 10-May-2022

[name]

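### The Step 1 participation weights leave out baseline (T0) quality of life, so the weighted comparison of QoL change between treatment groups may leave arm-differential loss related to T0 QoL uncorrected

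*SAP*

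**What the plan says.** Objective 2 (SAP section 1) is "To compare change from baseline in quality of life" at F1, by treatment group and by clinical outcome group. The sensitivity analysis in section 5.1 is meant to represent children with no F1 data. The plan expects many of them: "It is anticipated that 25% of the original sample of 201 children will have follow-up outcomes missing".

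Step 1 says: "Inverse probability weights will be calculated by treatment group using the whole sample of 201 children". It is built by "adopting a logistic regression model predicting participation at F1". The predictors are chosen "using the following baseline variables (with no missing values", and the list is "age at randomisation and SPT wheal size, clinical outcome at T2 (SU, DWSU without SU or Allergic". No QoL score appears.

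T0 QoL is used elsewhere. It is the starting value of outcome I (Table 1), and section 5.2 compares QoL "using a mixed model applied to the data at 4 timepoints (T0, T1, T3/F0, F1". Adjustment for baseline QoL in outcome I is placed with the comparisons between clinical outcome groups (sections 5.1 and 5.2). The treatment-group model adjusts for age group and SPT wheal size.

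**The concern.** Inverse-probability weighting can only balance participants and non-participants on what is in the weight model and on whatever that carries with it. For a change score, the child's own starting value is an obvious variable that could relate both to staying in follow-up and to the outcome. If T0 QoL predicts participation differently in the arms, the participating children are no longer comparable at T0, and weights that ignore T0 QoL do not restore the balance.

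Little else in the plan would do so:

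- Multiple imputation in Step 2 covers F1 participants only, so it brings in nothing on absent children.
- The mixed model could borrow from T0 scores of children lost before F1, but section 3 limits the analysis to children with outcome data at F1.
- The baseline-QoL adjustment is not stated for the treatment-group comparison.

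At stake is how the sensitivity analysis is read. Agreement between weighted and available-case results for QoL change by arm would look reassuring without having tested this kind of loss.

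**Working it through.** **Inputs from the SAP.** Arms: "PPOIT n=79; OIT n=83; placebo n=39", and 79 + 83 + 39 = 201. Expected missing: 0.25 × 201 = 50.25, about 50 children. In placebo: 0.25 × 39 = 9.75, about 10.

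**Assumptions (the SAP gives no figures).** QoL is in SD units. The T0-F1 correlation r is 0.3 to 0.7. Participation is about 75%. The odds ratio (OR) for participation per SD of T0 QoL is 1.5 to 2. SU and DWSU rates by arm are illustrative. I take the weighted analysis to cover outcomes H and I. The plan states no figure for this bias, so there is none to reproduce.

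**Formula.** Let δ be the shift in mean T0 QoL among an arm's participants, and D the size of the difference in δ between PPOIT and placebo. If loss depends only on T0 QoL, the available-case bias in the arm difference has absolute size:

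- F1 score: r × D
- change score, unadjusted: (1 − r) × D
- change score adjusted for T0 QoL: 0

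If δ is the same in both arms, D = 0 and the difference is unbiased.

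**Large-sample simulation** (N = 400,000; weights fitted within arm on age, SPT and T2 outcome). Absolute bias in QoL change, PPOIT v placebo, SD units, available case / SAP weights:

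| Loss related to T0 QoL | r = 0.3 | r = 0.5 | r = 0.7 |
|---|---|---|---|
| Placebo only, OR 1.5 | 0.074 / 0.073 | 0.047 / 0.047 | 0.036 / 0.035 |
| Placebo only, OR 2 | 0.122 / 0.123 | 0.080 / 0.080 | 0.053 / 0.052 |
| Opposite directions, OR 1.5 | 0.137 / 0.137 | 0.100 / 0.100 | 0.057 / 0.057 |
| Opposite directions, OR 2 | 0.224 / 0.224 | 0.162 / 0.161 | 0.094 / 0.095 |

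With T0 QoL added by arm, the bias is at most 0.005 in every cell.

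The formula agrees. For opposite directions and OR 2 at r = 0.5, the F1-score bias was 0.157 and the change bias 0.162, so D = 0.157 + 0.162 = 0.319. It then predicts 0.7 × 0.319 = 0.223 at r = 0.3 (simulated 0.224) and 0.3 × 0.319 = 0.096 at r = 0.7 (simulated 0.094).

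**Where the SAP weights are adequate** (r = 0.5):

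- Same relation in all arms, OR 2: the bias in the F1 difference is 0.003 with or without T0 QoL, which is simulation noise. Only arm means shift (placebo mean 0.078 with SAP weights, −0.002 with T0 QoL added).
- Loss running through SU status: the bias in the F1 difference goes from −0.010 to 0.003 with the SAP weights.
- Change adjusted for T0 QoL, loss in placebo only, OR 2: −0.006 available case and −0.005 with SAP weights, against −0.005 with T0 QoL added.

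**Trial-size simulation** (79 v 39, r = 0.5, T2 outcome included, 2,000 trials). Absolute bias in QoL change; a dash means not run:

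| Weights | OR 2, PPOIT only | OR 2, opposite | OR 1.5, PPOIT only |
|---|---|---|---|
| None (available case) | 0.085 | 0.168 | 0.042 |
| SAP model | 0.084 | 0.168 | 0.043 |
| + T0 QoL, pooled, arm main effect only | 0.086 | 0.168 | – |
| + T0 QoL, pooled, arm-by-T0-QoL term | 0.006 | 0.010 | – |
| + T0 QoL, fitted by arm | 0.005 | 0.014 | 0.005 |

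The sampling SD of the difference was 0.225 v 0.225, 0.239 v 0.246 and 0.228 v 0.223 in the three scenarios. A separate run gave 0.080 available case, 0.080 with SAP weights and 0.003 with T0 QoL by arm; for opposite directions it gave 0.160, 0.161 and 0.010.

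**The case against.** The plan's short covariate list has a rationale. Step 1 admits only complete variables, and the SAP does not say that T0 QoL is complete in all 201 children. With about 10 placebo children lost, a by-arm model with an intercept, age, SPT and two terms for T2 outcome already has five coefficients. T2 outcome is the post-treatment variable most likely to link arm, QoL and staying in the study, and it is included. T0 QoL precedes treatment and families remain blinded, so a relation with loss that differs by arm beyond clinical outcome is a special case. Opposite directions are more special still. The available-case analysis is primary; this is a sensitivity analysis.

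Most of this stands as a limit on size and likelihood. It does not remove the gap, because a rule for missing scores and an interaction term deal with completeness and sparsity.

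Two stronger readings are tempting and are not supported:

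- A reader might infer that the weights cannot correct QoL-related loss at all and simply repeat the available-case bias. They do correct loss that runs through T2 outcome. The arm difference is essentially unbiased when loss relates to T0 QoL equally in every arm. Clinical-group comparisons of outcome I adjusted for baseline QoL are protected from loss that depends only on T0 QoL.
- A reader might infer that omitting study site is a comparable fault. Nothing in the SAP links site to participation. F1 is a phone call with diary-app monitoring (section 2.1), and no size can be given.

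**Conclusion.** The point holds in conditional form. The weight model omits a collected variable that is central to Objective 2. For the unadjusted comparison of QoL change between treatment groups, the weighted analysis matches the available-case analysis to within about 0.001 SD whenever loss depends on T0 QoL differently by arm, beyond age, SPT and T2 outcome.

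At r = 0.5 and odds ratios of 1.5 to 2, the bias is about 0.05 to 0.16 SD. Over r from 0.3 to 0.7 it runs from about 0.04 to 0.22 SD. At trial size and r = 0.5 it stays below one sampling SD: 0.043/0.228 = 0.19 for OR 1.5 in one arm, and 0.168/0.239 = 0.70 for OR 2 in opposite directions.

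The SAP cannot show whether such loss occurs, and every odds ratio and correlation here is assumed. If the sentence in section 5.2 on baseline-QoL adjustment for outcome I was also meant for the treatment-group model, that comparison would be protected from loss that depends only on T0 QoL, and the SAP should say so.

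**What to change.** Amend Step 1 in section 5.1 for the QoL outcomes:

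- Add the T0 QoL total score to the participation model.
- Keep fitting by treatment group. If the placebo model is unstable, use one pooled model with an arm-by-T0-QoL term. Do not use a pooled model with arm only as a main effect: it forces one T0-QoL slope on all arms and left the bias unchanged (0.086 and 0.168 SD).
- Because Step 1 is limited to complete variables, state that any missing T0 score is filled inside the weight model only, with the mean plus a missing indicator.

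The cost is a short change of wording and no new data. It adds one or two coefficients per arm to an already sparse model. In some scenarios the sampling SD rises slightly, by at most about 0.01 SD (0.246 − 0.239 = 0.007 in the worst case run).

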This occurs after completion of the T3 visit of PPOIT-003, which coincides with the first visit of the follow-on study (F0). All subjects will be followed up for 60 months after T3/F0 (which is up to 6 years post treatment that was received in PPOIT-003). During this time, all subjects will be monitored for information on exposure to peanut/amount of peanut being eaten and allergic reactions via a mobile diary application (app) until the end of study (72 months post treatment (F5)).

A phone call will be administered at the following time points:

• Time point F1 – 12 months after F0 (24 months post-treatment)

A visit for SPT, bloods and stool will be administered at the following time points:

- Time point F2 24 months after F0 (36 months post-treatment)
- Time point F3 36 months after F0 (48 months post-treatment)
- Time point F4 48 months after F0 (60 months post-treatment)
- Time point F5 60 months after F0 (72 months post-treatment)

Note: Where a face-to-face visit is not possible (eg due to COVID-19 restrictions or other unavoidable circumstances), the visit will be conducted by phone and SPT, bloods and stool test will not be performed.

This study is expected to run for 78 months from the start of participant enrolment to the last participant finishing the study. The length of the study (i.e. follow up period) for each participant is 60 months.

The three sites will be: The Royal Children's Hospital Melbourne / Murdoch Children's Research Institute, The Women's and Children's Hospital Adelaide, Perth Children's Hospital. A maximum of 201 participants will be recruited – the study population recruited to PPOIT-003.

Study population

Subjects meeting the eligibility criteria will be recruited at end of PPOIT-003 without unblinding of PPOIT-003 treatment allocation.

Inclusion criteria

Subjects are eligible for the study if they meet all of the following criteria:

- Were randomised and received at least 1 dose of treatment in PPOIT-003
- Participated in the PPOIT-003 randomised trial
- Written informed consent from participants and/or parent/guardian.

Exclusion criteria

Subjects are not eligible for the study if they meet any of the following criteria:

- Are taking probiotic supplements (does not include formula, yoghurts and fermented foods).
- Withdrew from the PPOIT-003 study.
- Have any condition that, in the opinion of the Investigator, precludes participation for reasons of safety.

Sample size

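### The IPW/MI sensitivity analysis is not fully executable as written and is fragile in the placebo arm

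*SAP*

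**What the plan says.** The sensitivity analysis in SAP section 5.1 has two steps.

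- **Step 1, weights.** The weights are "calculated by treatment group using the whole sample of 201 children adopting a logistic regression model predicting participation at F1". That model takes three predictors, which the SAP introduces in these terms: "using the following baseline variables (with no missing values): age at randomisation and SPT wheal size, clinical outcome at T2". The last of them has three classes (SU, DWSU, Allergic). After that, "only children whose parent/guardian consented for follow-up will included in the following step".
- **Step 2, imputation.** "Thirty completed data sets will be imputed using multivariate normal regression including all the participants who participated in the F1 follow-up". Each completed data set is then analysed with the Step 1 weights. No rule for rounding or truncating imputed values is given.

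Four other places bear on this:

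- Section 2.1 defines SU as passing both challenges, DWSU as passing T1 and failing T2, and Allergic as failing T1. It gives no class for a child without a T1 challenge, or for one who passed T1 and had no T2.
- The exclusion criteria in section 2.1 include "Withdrew from the PPOIT-003 study", and the general methodology in section 5.1 leaves children withdrawn from the parent trial out of every analysis.
- Section 2.1 gives the arms as "PPOIT n=79; OIT n=83; placebo n=39". Section 5.1 adds: "It is anticipated that 25% of the original sample of 201 children will have follow-up outcomes missing".
- Section 5.2 analyses binary outcomes A, B and D with a Gaussian linear-link model for the risk difference and a log-link Poisson model for the relative risk. It expects some of these outcomes to be rare.

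**The concern.** IPW/MI is the only sensitivity analysis the SAP plans for missing data, with about 50 of 201 children expected to be missing. Its purpose is to show whether the available-case results would change if those children were represented. That requires the weight model to contain them, the weights to be reasonably stable, and the completed data to fit the planned models. Each of these is in doubt.

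The first matters most. Children who withdrew from the parent trial are non-participants by design. If those without a challenge result drop out of the weight model unnoticed, close agreement between the sensitivity and primary results would say nothing about them.

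**Working it through.** **Inputs.** Arm sizes are from section 2.1: 79 + 83 + 39 = 201, which reproduces the SAP's total. The 25% loss is from section 5.1; an equal split across arms is assumed. The SAP gives no clinical outcome counts by arm and no outcome prevalences, so ranges are assumed for both.

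**1. The T2 predictor.** Take a child who withdrew from PPOIT-003 before the challenges. The child is one of the 201 but cannot enter the follow-on study and has no clinical outcome class. There are three simple ways to handle this:
- Let the logistic model drop the child. The weights then represent fewer than 201.
- Call the child Allergic. That contradicts the definition, which needs a failed T1.
- Add a no-result level. If it holds only withdrawals, nobody in it participates and nobody can be weighted up for it.

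Leaving withdrawn children out of all analyses also conflicts with fitting a model to all 201.

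**2. Separate fits by arm.** Age and SPT with one coefficient each, plus two for clinical outcome, make four slopes. Non-participants are 0.25 × n:
- PPOIT: 19.75, or 19.75/4 = 4.9 per slope
- OIT: 20.75, or 5.2 per slope
- Placebo: 9.75, or 2.4 per slope

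Two kinds of perfect prediction need to be kept apart. If everyone at an outcome level participates, the fitted probability tends to 1 and so does the weight. If nobody does, that level cannot be represented. For two placebo cells of size k:
- k = 3 (assumed): all in at least one cell, 1 − (1 − 0.75³)² = 67%; none in at least one, 1 − (1 − 0.25³)² = 3.1%
- k = 4 (assumed): 53% and 0.8%

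Simulation of the 39-child arm (200,000 draws, 25% loss) over assumed SU/DWSU shares:

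| SU/DWSU share | Some level all in | Some level all out |
|---|---|---|
| 2%/2% | 60% | 19% |
| 5%/5% | 73% | 17% |
| 10%/10% | 59% | 6% |
| 20%/20% | 26% | 0.3% |

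**3. Which children.** Step 1 models F1 participation but carries forward those who consented. Step 2 imputes for those who participated. A child who consented and then missed F1 is in the first set and not the second.

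**4. Normal imputation.** For a binary outcome of prevalence p, a marginal normal draw has mean p and variance p(1 − p). The share below zero is Φ(−p/√(p(1 − p))). If draws are rounded at 0.5, the imputed prevalence is 1 − Φ((0.5 − p)/√(p(1 − p))).

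| p (assumed) | Draws below 0 | Prevalence after rounding |
|---|---|---|
| 2% | 44% | 0.03% |
| 5% | 41% | 2.0% |
| 10% | 37% | 9.1% |
| 20% | 31% | 22.7% |

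Unrounded draws keep the expected mean at p. The shares refer to imputed cells only. With 10% of values missing (assumed) and p = 5%, rounding would move the overall prevalence to 0.9 × 5% + 0.1 × 1.95% = 4.7%.

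**The case against.** A reader might infer that the analysis cannot work at all. The documents do not support that, for five reasons:

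- **T2 predictor.** T2 comes before the follow-on study, and a post-randomisation variable is a legitimate predictor of participation. The SAP states that it is complete, and parent-trial documents not shown here may classify every child. This stands as far as it goes: no count of unclassified children is given, so omission is a risk and not a demonstrated loss. It does not explain how the stated completeness fits the section 2.1 definitions.
- **Placebo fit.** Separate fits are the likelier reading but are not stated outright. It is also tempting to add the two kinds of perfect prediction together, which gives 68% for cells of 3 and 3. Nearly all of that is the all-in case, which still yields weights near 1. This stands: the arithmetic shows instability, not certain failure.
- **Consent and participation.** Step 2 limits itself to F1 participants more than once, and its closing text treats non-participants and non-consenters as one group. This is mostly loose wording, but two statisticians could still select different children.
- **Normal imputation.** It touches only item-missing values among F1 participants, not the children who are absent. No rounding is specified, and unrounded values suit the Gaussian risk difference. This stands, and leaves the relative risk and the count and category outcomes as the problem.
- **Other protection.** For quality of life, the mixed model over four time points also uses partly observed children.

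**Conclusion.** The concern holds as a need for repair. The firmest part rests on the SAP's text alone: the weight model is meant to cover 201 children, its T2 predictor is undefined for any child without the challenges, and withdrawn children are excluded elsewhere. The size of the effect cannot be given, because the number without a T2 class is not stated.

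The placebo fit is fragile if done separately: about 10 non-participants for four slopes under an equal 25% loss. A level with no participants has a chance of about 0.3% to 19% over the assumed shares. The imputation fault is real for the log-link relative risk (37% to 41% of marginal draws negative at 10% and 5% prevalence), but is confined to item-missing values. The primary available-case analysis is unaffected, so this should be corrected but does not threaten the main results.

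**What to change.** 1. Replace the single weight with two stages: (a) the probability of completing PPOIT-003 among all 201, from treatment and true baseline variables such as age, SPT, site and screening quality of life; (b) the probability of F1 participation among completers, adding T2 clinical outcome. Multiply the two probabilities and invert. State how any completer without a class is handled, and reconcile the exclusion of withdrawn children with the 201-child target.
2. Fit each stage as one pooled model with treatment as a term.
3. Use one set, F1 participants, in both steps, and apply the weights only to them.
4. Impute by chained equations: logistic for binary outcomes, predictive mean matching for counts and scores. Name treatment explicitly in the imputation model and include T0 and T1 quality of life.

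The cost is SAP wording and some programming. The pooled model assumes that predictors act alike in all arms, a small price for steadier weights in a 39-child arm.

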5. STATISTICAL METHODOLOGY

5.1. F1 GENERAL METHODOLOGY

Outcomes will be analysed by treatment group, according to the group to which subjects were originally randomly allocated, regardless of subjects' compliance to treatment during the PPOIT-003 study, or crossover to other treatments. The following pairwise comparisons will be of interest:

- PPOIT vs Placebo
- PPOIT vs OIT
- OIT vs Placebo

Outcomes will also be described by the clinical outcome achieved at end of treatment in PPOIT-003 (T2 PPOIT-003), that is SU, DWSU without SU and Allergic. The following pairwise comparisons will be of interest:

(FORM: SAP template interim analysis/Version 1.1)

- SU vs DWSU
- SU vs Allergic
- DWSU vs Allergic

All demographic and continuous outcomes (collected at T0 and T3/F0) will be presented as mean and standard deviation (or medians and interquartile ranges for skewed data), whilst categorical outcomes will be presented as absolute and relative frequencies in the three treatment groups and clinical groups. Table of characteristics at T0 will be presented by treatment groups for those consented to roll over to PPOIT-003LT; Table of characteristics at T3/F0 will be presented both by treatment groups and by clinical outcome groups.

In this interim analysis, subjects who are withdrawn at the end of the PPOIT003 study will not be included in any analyses. All the outcomes will be reported in available cases who consented to roll over to PPOIT-003LT.

MEASURES OF TREATMENT EFFECT

Risk difference (RD) and relative risks (RR) between treatment groups (or clinical outcome groups) will be the measures of treatment effect for binary outcomes. Mean difference between treatment groups (or clinical outcome groups) will be the measure of treatment effect for continuous outcomes whose distribution is reasonably symmetrical. Median difference between treatment groups (or clinical outcome groups) will be the measure of treatment effect for continuous outcomes whose distribution is severely skewed.

ESTIMATION OF TREATMENT EFFECTS (BETWEEN TREATMENT GROUPS)

For binary outcomes, a generalized linear model (GLM) approach will be used and account for clustering by site, adjusted by the age group at randomisation (1-5 years; 6-10 years) and SPT wheal size (\leq 10mm; >10mm).

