5.2. F1 INTERIM ANALYSIS METHODOLOGY

Outcomes A, B, D

For these binary outcomes, they will be summarised as the number and proportion of children who had the outcome as yes between F0 and F1 by treatment groups and by clinical outcome groups.

The comparison between treatment groups will be made using a GLM approach with Gaussian error distribution (to avert convergence difficulties with low prevalence outcomes), linear link function and a cluster-robust standard error calculation to account for clustering by study site. The RD and 95% CI will be derived, adjusted by the age group at randomisation (1-5 years; 6-10 years) and SPT wheal size (≤10mm; >10mm).

The RR (with 95% CI) comparing treatments will also be estimated using a GLM approach (the "modified Poisson" approach of Zou, employing the Poisson family, a log link function and a cluster-robust standard error calculation to account for clustering by site), adjusted by the age group at randomisation (1-5 years; 6-10 years) and SPT wheal size (≤10mm; >10mm).

The comparison between clinical outcome groups will be made using a binary regression model. The RD, RR and 95% CIs will be derived.

Outcome C, F, G

For these categorical outcomes, they will be summarised as the number and proportion of children who had the outcome in each category by treatment groups and by clinical outcome groups. They will also be summarised as the median, IQR and range by treatment groups and by clinical outcome groups.

Outcomes C, E, F, G, I

For these continuous outcomes, they will be summarised as mean and SD or median and IQR by treatment groups and by clinical outcome groups as specified.

The mean difference between treatment groups will be obtained by using GLM to account for clustering by site, adjusted by the age group at randomisation (1-5 years; 6-10 years) and SPT wheal size (≤10mm; >10mm). The median difference using quantile regression model to adjust for the stratification factors if not normally distributed.

The mean difference between clinical outcome groups will be obtained by using a linear regression model. The median difference using quantile regression model if not normally distributed. For outcome I, linear/quantile regression model will be used for further adjusted for baseline QoL score.

Outcome H

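### The age subgroup analysis looks at each band separately with no treatment-by-age interaction, so it gives no valid estimate of whether effects differ by age

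*SAP*

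**What the plan says.** SAP section 5.1, under the sub-group heading, gives one sentence: "Available cases will be analysed by subgroups according to their age group at screening of PPOIT003 (0-5 years / 6-10 years", applied to all outcomes.

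The treatment-group models use a different age variable. They are "adjusted by the age group at randomisation (1-5 years; 6-10 years) and SPT wheal size" in section 5.1, and section 5.2 repeats this for the binary and continuous outcomes. The quantile regression wording treats these covariates as the randomisation strata: "The median difference using quantile regression model to adjust for the stratification factors if not normally distributed". The mixed model for quality of life is specified "with fixed effects for treatment, age group at randomisation and SPT wheal size". In all of these, age group enters as a main effect only.

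The comparisons between clinical outcome groups (SU, DWSU, allergic) use binary, linear or quantile regression with no age term. The only adjustment stated for them is baseline quality-of-life score, for outcome I.

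The SAP contains no interaction term, heterogeneity test or multiplicity rule, and does not label the subgroup results exploratory. It does not say whether the age covariate is dropped inside a band.

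**The concern.** The usual reason to split results by age is to see whether the effect depends on age. That question needs an estimate of the difference between the bands with its own confidence interval. The plan produces an effect and interval in each band and stops, so a reader can only compare the two by eye. One interval excluding no effect while the other includes it is not evidence that the effects differ. The smaller band has less information, and both have less than the whole sample.

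At stake is how the age results are read. The subgroup covers nine lettered outcomes, three treatment contrasts and three clinical-group contrasts, so there is ample room for chance contrasts between bands.

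A smaller gap concerns the treatment-group models. Inside a band the age-stratum covariate is constant, apart from any child whose two age definitions disagree, and the analyst is not told what to do with it.

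**Working it through.** **Inputs from the SAP.** Maximum arm sizes are "PPOIT n=79; OIT n=83; placebo n=39" (section 2.1). On loss: "It is anticipated that 25% of the original sample of 201 children will have follow-up outcomes missing" (section 5.1). A two-sided 5% level is implied by the 95% intervals, for example "The RD and 95% CI will be derived" (section 5.2). There are three sites (section 2.1). The SAP gives no power, effect size or age split.

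**The plan's own figure.** 79 + 83 + 39 = 201, which reproduces. There is no power calculation to reproduce.

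**Assumptions.** Whole-sample power of 50%, 80% or 90% for a given contrast; a share *f* of children in one band of 0.5, 0.4 or 0.3; the same true effect in both bands; normal approximation.

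**Chance of exactly one significant band.** The standardised whole-sample effect is d = 1.960 + z(power), which is 1.960, 2.802 and 3.242 for power of 50%, 80% and 90%. Power in a band with share *f* is p = Φ(d√f − 1.960). The chance that exactly one band is significant is p₁(1 − p₂) + p₂(1 − p₁).

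| Whole-sample power | Split | p₁ | p₂ | Exactly one band significant |
|---|---|---|---|---|
| 50% | 50/50 | 0.283 | 0.283 | 0.406 |
| 50% | 40/60 | 0.236 | 0.329 | 0.410 |
| 50% | 30/70 | 0.188 | 0.374 | 0.422 |
| 80% | 50/50 | 0.508 | 0.508 | 0.500 |
| 80% | 40/60 | 0.425 | 0.583 | 0.512 |
| 80% | 30/70 | 0.335 | 0.650 | 0.549 |
| 90% | 50/50 | 0.630 | 0.630 | 0.466 |
| 90% | 40/60 | 0.536 | 0.709 | 0.485 |
| 90% | 30/70 | 0.427 | 0.774 | 0.540 |

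The range is 0.41 to 0.55. With no effect in either band it is 2 × 0.05 × 0.95 = 0.095.

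**What an interaction term can deliver.** Its nominal false-positive rate is 5% per contrast, but its precision is poor. With an even split, each band estimate has twice the whole-sample variance, so their difference has four times that variance and twice the standard error. For an interaction as large as a main effect that has 80% power, power is Φ(2.802/2 − 1.960) = Φ(−0.559) = 0.29.

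In SD units, after 25% loss, the arms are 79 × 0.75 = 59.25, 83 × 0.75 = 62.25 and 39 × 0.75 = 29.25. The difference detectable with 80% power overall is 2.802 × √(1/n₁ + 1/n₂). An even split multiplies this by √2 within a band and by 2 for the interaction:

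- PPOIT vs OIT: 0.51 overall, 0.72 within a band, 1.02 for the interaction.
- PPOIT vs placebo: 0.63, 0.90, 1.27.
- OIT vs placebo: 0.63, 0.89, 1.26.

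**Three sites.** Section 5.2 uses cluster-robust standard errors by site for the binary outcomes. A simulation of that linear model with the interaction added and no true effect (assumed: 150 children, arms of 29, 62 and 59, 30% event rate, even age split) rejected in about one trial in five with a normal reference. With a t reference on 2 degrees of freedom it rejected in about 6%.

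**Age definitions.** The subgroup uses 0-5 and 6-10 years at screening. The covariate is "adjusted by the age group at randomisation (1-5 years; 6-10 years". Both cut between 5 and 6 years. They can disagree only for a child who turned 6 between screening and randomisation. A child under 1 would fall outside the covariate's bands. The SAP counts neither.

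**The case against.** The best defence is that the SAP promises little. Effect modification by age is not among the objectives in section 1. The subgroup sentence plans no comparison between bands, no significance threshold and no claim about age, and results come as estimates with intervals. A reader might infer that the plan intends to call a result in one band alone an age effect. The text does not say so, and the discordance figures describe a misreading that the output permits, not an analysis that is planned. They would also apply to any trial split in two, and the power and age split behind them are assumed.

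A reader might also infer that the two age definitions cause the chance differences. They do not: the missing interaction is the cause, and the definitions are largely a labelling inconsistency. Nor do all models adjust for age; the clinical-outcome-group models have no age term, so the constant-covariate question does not arise there. Finally, adding an interaction does not by itself secure a 5% error rate with three clusters.

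All of this stands and limits the point. It does not remove it. The SAP gives the subgroup method as separate analysis by band for every outcome, and that method cannot show whether effects differ by age.

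**Conclusion.** The point holds as a gap in method. The separate-band analysis yields no valid estimate of effect modification by age, for either the treatment comparisons or the clinical-group comparisons. Informal comparison would find exactly one significant band in about 41% to 55% of cases under an identical effect. That rests on assumed whole-sample power of 50% to 90%, splits from 50/50 to 30/70 and the normal approximation. The facts about the text are certain; the harm depends on how the results are read. The age-definition mismatch is a side note: it bears only on the treatment-group models, and only on children under 1 or those who turned 6 between screening and randomisation.

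**What to change.** - For each outcome that is modelled, fit one model on all available cases with a treatment-by-age-stratum term. For the comparisons between clinical outcome groups, include age stratum and a clinical-group-by-age term.
- Report each interaction estimate with its 95% CI, and take the within-stratum effects from the same model. For binary outcomes, name the scale (RD or RR), because an effect can be constant on one and vary on the other.
- Use standard errors that suit three sites, for example site as a fixed effect in place of cluster-robust errors on three clusters. Otherwise state that the 5% level is nominal.
- Label the age results exploratory and state that the interaction is estimated with low precision.
- Use one age definition throughout, the randomisation stratum (1-5 and 6-10 years). The question of a constant covariate inside a band then disappears.

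The cost is SAP wording and an added interaction in each model (with the age main effect in the clinical-group models). No new data are needed. The drawback is wide interaction intervals, which show how little this sample can say about age.
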